7.4.2.11 Dose administration record

Full and complete imatinib (Glivec[®]) dosing data from medical charts/ prescription records (historic and/ or current) should be recorded, if available. Detailed information including total daily dose, regimen and dose changes (e.g. dosing errors) to be captured wherever possible.

7.5 Study size

This is a multi-center, observational registry that is not designed to test a formal hypothesis and therefore there is no formal sample size calculation. The registry has a planned enrollment of a minimum of 50 patients.

7.6 Data management

7.6.1 Data collection methods and tools

Designated staff will enter the data required by the registry into a secure web-based internet system using a Novartis-designed eCRF with fully validated software that conforms to 21 CFR Part 11 and regulatory requirements for electronic data capture (EDC). Registry site staff will not be given access to the EDC system until they have been trained. An international Contract Research Organization (CRO) will administer and manage the web-based system and review the data for completeness and accuracy.

Each subject in the study is uniquely identified by a **9 digit subject number** which is a combination of his/ her **4-digit center number** and **5-digit subject number**. The center number is assigned by Novartis to the registry site. Upon signing the informed consent form, the subject is assigned a subject number by the treating physician and/ or designee. For studies using electronic CRFs, only the assigned 5-digit subject number (excluding the leading zeros)

should be entered in the field labeled "Subject ID" on the EDC data entry screen. Once assigned to a subject, a subject number will not be reused.

The Principal Investigator is responsible for assuring that the data entered into eCRF is complete, accurate, and that entry and updates are performed in a timely manner.

Novartis personnel (or designated CRO) will review the data entered by registry staff for completeness and accuracy. Electronic data queries stating the nature of the problem and requesting clarification will be created for discrepancies and missing values and sent to the registry site via the EDC system. Designated registry site staff is required to respond promptly to queries and to make any necessary changes to the data. Queries are expected to be minimal since the web-based system will have automatic validation programs to check for data discrepancies in the eCRFs and, allow modification or verification of the entered data by the registry site staff.

Concomitant treatments and prior medications entered into the database will be coded using the WHO Drug Reference List, which employs the Anatomical Therapeutic Chemical classification system. Medical history/current medical conditions and adverse events will be coded using the Medical dictionary for regulatory activities (MedDRA) terminology.

At the conclusion of the study, the occurrence of any protocol deviations will be determined. After these actions have been completed and the data has been verified to be complete and accurate, the database will be declared locked and made available for data analysis. Authorization is required prior to making any database changes to locked data, by joint written agreement between the Global Head of Biostatistics and Data Management and the Global Head of Clinical Development.

For EDC studies, after database lock, the investigator will receive a CD-ROM or paper copies of the patient data for archiving at the investigational site.

Further information on quality control, data quality assurance, data recording and document retention and site monitoring are explained in Section 7.8.

7.6.1.1 Treating physician / investigator

Treating physician and/ or designated registry staff are responsible for providing adequate patient care and accurate patient data. The following are data handling responsibilities for the treating physicians and/ or their designated staff:

- Record and maintain accurate patient data in medical charts, research records or files.
- Record and ensure patient data entered into the registry is accurate; obtain missing data and clarify discrepancies with the treating physicians and/ or their designated staff on an ongoing basis.
- Provide missing information and responses to queries to clarify discrepancies (as required).
- Enter, update and complete registry data collection pages on an ongoing basis, the data will be subsequently transferred electronically to the Novartis global clinical team.
- Enter and/ or update patient registry data a minimum of once yearly (12 ±2 month intervals) for the duration of the registry (if necessary).

- Ensure all AE information is included in the individual patient eCRFs which must be updated in the registry database on a periodic basis, but not later than one month of new information becoming available.
- Contact Novartis CMO&PS office in their local country regarding SAEs, and provide information on SAEs to investigators and/ or Novartis representative and/or designee as needed (as outlined in Section 9).

7.6.1.2 Novartis

Novartis responsibilities in regards to data handling are specified below:

Novartis global clinical study team

- Development of electronic Case Report Form.
- Ensure all patients are assigned a unique patient number.
- Review and check the registry database for missing data, inconsistencies, and any obvious discrepancies.
- Contact the treating physician and/ or designee, for updated information; any queries generated will be documented.
- Process and record in the database any discernible manual protocol deviations.
- Archive data according to Novartis standard operating procedures.

Novartis Chief Medical Office and Patient Safety

• Contact treating physician and/ or designee, or Novartis representative and/ or designee for SAE information or additional follow-up, as needed (as outlined in Section 9).

7.7 Data analysis

All analyses will be performed by a Novartis representative and/or designee.

All data summaries and analyses will have descriptive purposes only with no formal inferential testing.

Due to the observational nature of this registry, it is expected that some specific endpoints may not be available at all time points and for the entire population. Unless otherwise specified in the Reporting Analysis Plan, the analyses will be performed on available data.

Patient efficacy, safety and tolerability outcomes of patients treated with chemotherapy + imatinib will be summarized overall, by HSCT (yes/no) and by risk group (good-risk/induction-responder) / (poor-risk/induction non-responder).

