7.3.1.6 Time to transplant, time to engraftment, engraftment failure, graft versus host disease

- Time to transplant is defined from the date of diagnosis until the date of the transplant procedure.
- Time to engraftment (neutrophil, platelet and both neutrophil/platelet engraftment) is defined as the time from the date of transplant to the date of engraftment.
- Engraftment failure is defined as either definitive engraftment failure or the absence of engraftment.
- Presence/ absence of graft versus host disease; chronic or acute (Section 7.4.2.6).

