7.4.2.2 Induction response

The patient response to induction treatment provides a measure of the patient-risk category. The commonly used definitions of good-risk (induction-responder) / poor-risk (induction non-responder) suggested below are adopted from Biondi et al. 2012. If this is not the definition that was used for a patient, information will be obtained with respect to the definition of risk.

- Good-Risk Group: Patients with both early response and complete remission at the end of induction e.g. Blast cell count < 1000/µl in peripheral blood after 7 days of Prednisone given in combination with chemotherapy drug(s) before induction is instituted or have M1/M2 BM at day 15 (after start of chemotherapy) or M1 BM at day 21 and achieve CR after induction period.
- Poor-Risk Group: Patients with poor early response to induction treatment or absence of complete remission at the end of induction e.g. Blast cell count ≥ 1000/µl in peripheral blood after 7 days of Prednisone given in combination with chemotherapy drug(s) before induction is instituted or have M3 BM at day 15 or M2/M3 BM at day 21 or do not achieve CR after induction period.
 - M1: <5% blasts, counting all nucleated cells, including erythropoiesis. In case of regenerating marrow with a high erythropoietic predominance, at least a total count of 100 non-erythropoietic cells should be counted.
 - M2: 5-25% blasts, counting all nucleated cells, including erythropoiesis. In case of regenerating marrow with a high erythropoietic predominance, at least a total count of 100 non-erythropoietic cells should be counted.
 - M3: >25% blasts in a BM aspirate.

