7.7.4.1 Primary endpoint

The **primary endpoint** will be event-free survival (EFS) considering the following events: relapse at any site, development of a second malignant neoplasm or death.

Event free survival is defined as the time from diagnosis to the earliest of these events.

Censoring date will be the date of last contact for patients who did not experience any of these events.

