7.7.4.2 Main secondary endpoints

The main secondary efficacy endpoint will be overall survival (OS).

OS is defined as the time from diagnosis to death from any cause.

Censoring date will be the date of last contact for patients who are still alive.

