7.7.4.4 Methods of analysis

The efficacy endpoints will be summarized descriptively for the FAS.

Time to event endpoints (OS, EFS, transplant, engraftment) will be described using Kaplan Meier plots and associated statistics such as estimated survival rates by time points and medians along with 95% confidence intervals.

Event rates will be provided with 95% confidence intervals using Pearson-Clopper method.

On top of these analyses, analyses with a different definition of endpoint or on different subgroups will be performed:

- Analyses of OS and EFS will be performed taking into account the occurrence of transplantation procedure (by censoring at time of transplant for example). This is to avoid that prolongation in time to event after transplantation is taken as an Imatinib success.
- OS and EFS will be performed on the following subgroups:
 - subgroups based on age (with age categories selected to allow pubertal vs prepubertal differentiation),
 - subgroups based on peripheral lymphoblast count,
 - subgroups based on enrollment into approved clinical studies
 - subgroups based on type of transplant donor
- Time to transplant will be analyzed and presented according to type of transplant donor (autologous, allogeneic, syngeneic, other).

In addition, an analysis will be performed to evaluate the influence of prognostic factors (age, leukocyte count and early response, type of donor etc.) on efficacy outcome: these could include analyses of the impact of prognostic factors either on the odds of non-response to induction therapy by using logistic regression modeling or on time to event variables using cox regression modeling.

The association between MRD with other endpoints such as OS and EFS will be explored.

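### EFS and OS are counted from diagnosis but split by HSCT (yes/no), which is settled only later, so the two curves separate even if HSCT has no effect

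*Protocol*

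**What the plan says.** Section 7.7 states that efficacy, safety and tolerability outcomes "will be summarized overall, by HSCT (yes/no) and by risk group"; the data-analysis row of the abstract says the same. Section 7.7.4.4 adds OS and EFS analyses in "subgroups based on type of transplant donor".

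The clock for both survival endpoints starts at diagnosis. Section 7.7.4.1: "Event free survival is defined as the time from diagnosis to the earliest of these events". Section 7.7.4.2: "OS is defined as the time from diagnosis to death from any cause".

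Transplantation lies after that origin. Section 7.3.1.6 makes the delay an endpoint of its own: "Time to transplant is defined from the date of diagnosis until the date of the transplant procedure".

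For the HSCT split the protocol states no landmark, no time-dependent coding and no later start of the clock. It does not say whether a transplant given after relapse counts as yes. Section 7.7.4.4 does plan additional OS and EFS analyses that allow for transplantation, with censoring at transplant as the example. Their stated purpose is to keep a post-transplant gain from being credited to imatinib.

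**The concern.** Two distortions act on the HSCT split, in opposite directions.

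1. **Guarantee (immortal) time.** To be in the yes group a patient must live until the transplant and, for a transplant in first remission, stay event-free until then. A patient who was heading for HSCT but relapsed or died first is counted as no. The yes curve is too high and the no curve too low.
2. **Transplant after the event.** A patient who relapses and is then transplanted is also a yes, although the EFS event came before the transplant. For EFS this pulls the yes curve down and lifts the no curve.

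The sign and size of the displayed difference then depend on transplant timing and on the share of post-relapse transplants. HSCT yes/no is one of only two splits named for all outcomes, so readers will look at these curves and may take the gap as information about transplantation.

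**Working it through.** The protocol gives no figure for this split, so there is nothing to reproduce. The check asks what the planned display would show if HSCT had no effect.

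**Inputs**
- EFS 69.6% and OS 83.6% at 48 months (section 5.3.1, cohort 5 of the earlier study), used only for calibration.
- Horizon 60 months (the minimum follow-up is 5 years from start of imatinib).
- Assumed, because the protocol gives neither: wait from diagnosis to HSCT `t` = 3 to 12 months; share heading for HSCT `p` = 30% to 80%.
- Constant hazard.

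**Calibration**
- EFS: `h = -ln(0.696)/48 = 0.00755` per month; `S(60) = exp(-60h) = 63.6%` for everyone.
- OS: `h = -ln(0.836)/48 = 0.00373` per month; `S(60) = 79.9%`.

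**Step 1: only transplants before an event count**
- `yes = S(60)/S(t)`
- `no = (1-p)·S(60) / [(1-p) + p·(1-S(t))]`

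Example for EFS with `t` = 6 and `p` = 0.5: `S(6) = 0.9557`, so yes = 0.6357/0.9557 = 66.5% and no = 0.5·0.6357/(0.5 + 0.5·0.0443) = 60.9%.

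| t (months) | p | EFS yes | EFS no | gap | OS yes | OS no | gap |
|---|---|---|---|---|---|---|---|
| 3 | 0.3 | 65.0% | 63.0% | 2.1 | 80.8% | 79.6% | 1.3 |
| 6 | 0.5 | 66.5% | 60.9% | 5.6 | 81.7% | 78.2% | 3.5 |
| 12 | 0.8 | 69.6% | 47.2% | 22.4 | 83.6% | 68.0% | 15.6 |

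Gaps are in percentage points, taken before rounding. The true gap is zero in every row.

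**Step 2: transplants after an EFS event also count as yes**

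Take `p` = 0.4 and `t` = 6.5 months, so `S(6.5) = 0.952`. Per patient enrolled:
- transplanted before any event: 0.4·0.952 = 0.381, of whom 0.4·0.6357 = 0.254 are event-free at 5 years;
- event within 5 years without an earlier transplant: 0.4·0.048 + 0.6·0.364 = 0.238;
- never transplanted and event-free at 5 years: 0.6·0.6357 = 0.381.

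If a share `q` of the 0.238 is transplanted afterwards, `yes = 0.254/(0.381 + 0.238q)` and `no = 0.381/(0.619 - 0.238q)`.

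| q (assumed) | EFS yes | EFS no |
|---|---|---|
| 0 | 67% | 62% |
| 10% | 63% | 64% |
| 40% | 53% | 73% |
| 60% | 49% | 80% |

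The order reverses at a modest `q`, again with no HSCT effect.

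**Step 3: donor type**

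Everyone in a donor group has been transplanted, so with pre-event transplants only, each curve is `S(60)/S(t)`. Equal 6-month waits give 66.5% in every donor group: above the true 63.6%, but no difference between donors. Waits of 3 and 12 months give 65.0% and 69.6%, a false difference.

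**Step 4: does the remedy remove the artefact?**

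A simulation (20,000 registries of 50 patients, 60 months, waits uniform over 2-6 or 4-12 months, `p` = 30%, 50% or 80%) compared event-rate ratios under no effect. With the fixed flag and pre-event transplants only, the ratio was 0.52 to 0.89 for EFS and 0.54 to 0.90 for OS. With person-time before HSCT counted as untransplanted, it was 0.99 to 1.01 throughout. With a 12-month landmark, both groups have the same 5-year EFS among patients event-free at 12 months: S(60)/S(12) = S(48) = 69.6%.

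**The case against.** **The analyses are descriptive, and no objective compares HSCT with no HSCT.** True. Table 6-1 contains no such comparison, section 7.7 rules out formal testing, and the overall EFS and OS estimates do not use the split. This limits the seriousness. It does not remove the problem, because the curves and 5-year rates are themselves displaced.

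**With 50 patients the artefact is inside the noise.** For `p` = 0.4 and `t` = 6.5 there are about 19 yes and 31 no patients. The standard error of the 5-year difference is about √(0.668·0.332/19 + 0.616·0.384/31) = 14 points, against a bias of about 5. That stands for this case, but wide intervals do not correct a systematic shift, and the upper end of the range is well beyond 5 points.

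**Section 7.7.4.4 already allows for transplantation.** It does, and the wording leaves other methods open. But these are additional analyses with a different purpose, and they do not change who is placed in the yes and no groups.

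**Landmarks and time-dependent coding belong in the analysis plan.** Generally so. Here, however, the protocol itself fixes the grouping, and a plan that carries it out as written reproduces the bias.

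**Stronger readings that the text does not support.** A reader might infer that donor groups must differ falsely from one another; Step 3 shows that this needs unequal waits. A reader might extend the criticism to MRD, but "The association between MRD with other endpoints such as OS and EFS will be explored" fixes no method. A reader might also object that early response or donor type would enter a model "on the odds of non-response to induction therapy by using logistic regression modeling". Section 7.7.4.4 gives one illustrative factor list for alternative models and does not assign those factors to that one. Nor would early response predict the outcome perfectly: the poor-risk definition in section 7.4.2.2, "Patients with poor early response to induction treatment or absence of complete remission at the end of induction", still admits good early responders who miss remission.

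**Conclusion.** The concern holds for the HSCT (yes/no) split of EFS and OS. If only pre-event transplants count, the false 5-year gap in favour of yes is about 2 to 22 points for EFS and 1 to 16 for OS, with 5.6 and 3.5 points in the central case. If post-relapse transplants also count, which the wording allows, the EFS comparison can vanish or reverse: from 63% vs 64% to 49% vs 80% as the share transplanted after an event goes from 10% to 60%. Donor-type curves from diagnosis are each too high, but differ falsely between donors only if waits differ.

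The mechanism follows from the protocol's definitions. The sizes rest on assumed waits, shares and a constant hazard, so only the ranges should be relied on. It would go too far to infer that the registry's primary result is compromised: overall EFS and OS are untouched. This is a point that should be fixed, not one on which the study stands or falls.

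**What to change.** Change the analysis wording in section 7.7, the abstract and section 7.7.4.4:

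- For EFS and OS, replace the fixed HSCT (yes/no) split by one of two options. Either treat HSCT as a time-dependent state (Simon-Makuch curves, Cox model with a time-dependent covariate), or use one prespecified landmark from diagnosis, grouping patients still at risk by their HSCT status at that time.
- State that a transplant after an EFS event does not count in EFS groupings.
- Start the EFS and OS curves by donor type at the date of transplant.
- Keep the transplant-censoring analysis for its own purpose, and do not present it as a repair of the split.

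No new data are needed: section 7.4.2.6 already collects the date and phase of transplantation. The cost is precision and some complexity. A landmark drops patients with earlier events and widens intervals, which matters with about 50 patients. The time-dependent approach keeps all patients, but its curves cannot be read as the outcome of a fixed group followed from diagnosis and need a sentence of explanation.

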7.7.1 Analysis sets

The Full analysis set (FAS) comprises all patients who received at least one dose of imatinib + chemotherapy in the observational period.

The Safety set consists of all patients who received at least one dose of imatinib and with a valid post-baseline assessment. The statement that a patient has no AE constitutes a valid safety assessment. The occurrence of a death also constitutes a valid safety assessment. The safety set will be the population used in the assessments of safety. Patients with no post-baseline safety assessment will be listed.

7.7.2 Patient demographics/ other baseline characteristics

Demographic and other baseline data will be summarized descriptively. Categorical data will be presented as frequencies and percentages. For continuous data, mean, standard deviation, median, minimum, and maximum will be presented.

7.7.3 Treatments (study treatment, concomitant therapies)

Time on imatinib, duration of exposure, percentage of days on treatment, average dose intensity, and actual daily dose will be summarized using descriptive statistics for the Safety Set.

Chemotherapy exposure will be summarized using descriptive statistics for the Safety Set

Time on imatinib is defined as the time from first dose of imatinib to last dose of imatinib.

Duration of exposure to imatinib is defined as the time on imatinib minus the days with zero dose.

7.7.4 Efficacy analyses

The efficacy analyses will be performed using the FAS.

7.7.4.1 Primary endpoint

The **primary endpoint** will be event-free survival (EFS) considering the following events: relapse at any site, development of a second malignant neoplasm or death.

Event free survival is defined as the time from diagnosis to the earliest of these events.

Censoring date will be the date of last contact for patients who did not experience any of these events.

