7.3.1.2 Overall survival

• Overall survival is defined as time from diagnosis to death from any cause. i.e.Death information:- date and major cause (if applicable).

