Follow-up Visit			1	2	601	777	602	778	888
Obtain Informed Consent	D	8	Х						
Patient history				-					
Inclusion/ exclusion criteria	D	7.2.2	Х						
Demography	D	7.4.2.1	Х						
Relevant medical history / current medical conditions	D			х					
Prior / Concomitant medications	D			х	Х	x			
Concomitant antineoplastic therapy	D			Х	Х	Х			
History and diagnosis of disease	D			Х					
Induction Response [Poor / Good]	D	7.4.2.2		х					
Physical examination									
General Physical Examination	S	7.4.2.7		Х	Х	Х	Х	Х	
Performance status	D	7.4.2.8		Х	Х	Х	Х	Х	
Vital Signs [Height / Weight]	D	7.4.2.9		Х	Х	Х	Х	Х	
Development & Growth [Tanner Staging]	D	7.4.2.10		х	Х	x	x	X	
Laboratory assessments	•		•	•				-	
Response status [Efficacy]	D	7.4.2.3		Х	X	X	Х	X	

Novartis Non-interventional study protocol – v02 (Clean)

Confidential

Page 25 STI571 / Glivec[®] / CSTI571I2201

			مة	_	Surveillance	Period			
	ategory	Protocol	creening .	agnosis i aseline	On Treatment Follow-Up	End of study Treatment (EOT)	Post- Treatment Follow-Up	Study Evaluation Completion	Survival follow-up
	ů	Section	ы К	Di B	Visit Dates	EOT Date	Visit Dates	EOS Date	SURV Visit
Follow-up Visit			1	2	601	777	602	778	888
Hematology	D	7.4.2.4		Х	Х	Х	Х	Х	
BM assessment / cytogenetics	D			Х	Х	Х	Х	Х	
MRD assessment	D	7.4.2.5		Х	Х	Х	Х	Х	
Extramedullary involvement [Cerebro-spinal Fluid Exam]	D			х	х	х	Х	х	
Safety									
Adverse events / Serious adverse events	D	7.3.1.8		Х	Х	х	Х	Х	
Drug administration (imatinib dosing)	D	7.4.2.11		Х	Х				
Surgery									
Transplantation and engraftment [Hematopoietic Stem Cell Treatment (HSCT)]	D	7.4.2.6			X	X	X		
End of study treatment (EOT)	D					X			
Study Evaluation Completion	D							X	
Overall Survival	D	7.3.1.2							Х

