7.4.2.3 Efficacy response

The efficacy of treatment with chemotherapy in combination imatinib (Glivec[®]) will be evaluated from diagnosis, and based on the tests performed (e.g. extramedullary, cerebrospinal fluid exam, hematological, MRD assessment data) by the treating physician and/ or designee for each patient to assess incidence of relapse and secondary malignancy.

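### EFS is censored at last contact, but the survival visit records only death, so patients known only to be alive count as free of relapse and second malignancy

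*Protocol*

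**What the plan says.** Section 7.7.4.1 defines the EFS events as "relapse at any site, development of a second malignant neoplasm or death", timed from diagnosis, and sets the censoring rule: "Censoring date will be the date of last contact for patients who did not experience any of these events". Section 7.7.4.2 uses the same date for OS: "Censoring date will be the date of last contact for patients who are still alive". Nothing in the protocol ties last contact to a disease assessment.

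In Table 7-1 (Section 7.4.1) the column headed "Survival follow-up" (visit 888) is marked for one row only, "Overall Survival D 7.3.1.2". Section 7.3.1.2 describes that item as "Death information:- date and major cause (if applicable").

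The row that carries relapse and second malignancy begins "Response status [Efficacy". It refers to Section 7.4.2.3, whose stated purpose is "to assess incidence of relapse and secondary malignancy". It is marked at visits 2, 601, 777, 602 and 778, and not at 888. Hematology, marrow/cytogenetics, MRD, CSF and adverse events are also unmarked at 888.

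**The concern.** Last contact suits OS, because any contact settles whether the patient is alive. It suits EFS only if the contact also settles whether the patient has relapsed or developed a second malignancy. Visit 888 is a scheduled contact that does not.

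After visit 778 two of the three EFS components have no scheduled collection, while the third, death, still has. Time at risk keeps accruing. A relapse that ends in death is counted late, at the death, and a relapse that the patient survives is not counted. EFS therefore drifts towards OS. The registry is single-arm without a contemporary external control (Section 7.9), so the EFS estimate is itself the primary result.

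**Working it through.** **No figure to reproduce.** Section 7.5 gives no sample size calculation, and no EFS precision is stated.

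**Who is exposed.** Post-treatment follow-up (602) and study evaluation completion (778) both collect full disease status. Sections 7.1.1, 7.1.4 and 7.4.1 plan at least 5 years of follow-up from the start of imatinib. A patient followed as planned therefore has disease status to about year 5. Two kinds of time remain exposed:
- Time after visit 778. Five years is a minimum. Entry through a clinical trial is allowed from January 2012, and the final report is planned for June 2022, so some curves may run well past 5 years.
- Time after early discontinuation in a living patient who is still contacted for survival. Of the reasons in Section 7.2.5, death is itself an event, loss to follow-up brings no later contact, and consent withdrawal normally ends collection. That leaves administrative problems, protocol deviation and completed treatment.

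**Illustration of size at 5 years.**

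Inputs from the protocol (Section 5.3.1, cohort 5 of the pivotal study): EFS 69.6% and OS 83.6% at 48 months.

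Assumptions:
- Hazards are constant.
- Death without prior relapse occurs at d = 0.02 per year (range tried 0.01 to 0.03).
- A share f of patients, if still event-free at year T, becomes survival-only at T, regardless of prognosis.
- No relapse or second malignancy is recorded after T. This is a worst case.

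Steps:
1. EFS hazard λ = −ln(0.696)/4 = 0.0906 per year. True 5-year EFS S(5) = exp(−5 × 0.0906) = 63.6%. S(2) = 0.834 and S(3) = 0.762.
2. Non-fatal event hazard r = 0.0906 − 0.02 = 0.0706. The death hazard after relapse, m, is solved so that OS(4) = 0.836, giving m = 0.271. Here OS(t) = exp(−λt) + r[exp(−mt) − exp(−λt)]/(λ − m).
3. OS(3) = 0.887 and OS(2) = 0.933.
4. Expected 5-year Kaplan-Meier EFS under last-contact censoring = (1 − f)·S(5) + f·S(T)·OS(5 − T). The overstatement is f × [S(T)·OS(5 − T) − S(5)].
   - T = 2: 0.834 × 0.887 − 0.636 = 0.104
   - T = 3: 0.762 × 0.933 − 0.636 = 0.075

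| Share survival-only | Overstatement, from year 2 | Overstatement, from year 3 |
|---|---|---|
| 5% | 0.5 points | 0.4 points |
| 10% | 1.0 | 0.8 |
| 25% | 2.6 | 1.9 |
| 50% | 5.2 | 3.8 |

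Varying d from 0.01 to 0.03 moves the 50% row to 5.0-5.4 and 3.5-4.0. A simulation of 400,000 patients agrees to about 0.1 point.

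For scale, the 95% half-width at n = 50 is 1.96 × √(0.636 × 0.364/50) = 13 points.

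**Check of the remedy.** In the same model, censoring survival-only patients at their last known disease status, and not counting later deaths, gives 63.5-63.6% in every scenario, against a true 63.6%. If later deaths still count as events while survivors are censored back at T, living patients leave the risk set and those who die stay in it. The estimate is then too low: 61.7% and 58.3% (25% and 50% from year 2), 62.3% and 60.3% (from year 3). The rule must therefore say what happens to those deaths.

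**The case against.** The strongest reply is that the route to survival-only follow-up before year 5 is narrow. Stopping imatinib does not stop disease assessment, and the plan is 5 years of efficacy data for every patient. This stands. It confines the problem to the late curve and to a probably small group of early discontinuations.

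A reader might infer from Table 7-1 that EFS will be overstated by 2 to 5 points. The protocol does not support that. Those values need 25-50% of patients to be survival-only from year 2 or 3, and nothing in the text suggests such shares.

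A reader might also infer that no relapse information at all can arrive after visit 778. That is too strong. Section 7.1.1 asks for relevant follow-up information to be recorded and allows retrospective additions while the database is open, and the sources are hospital and clinical records. These routes are incomplete, however. None adds an item to visit 888. Section 9.1 requires adverse event monitoring for at least 30 days (or 5 half-lives, if longer) after the last dose and excludes documented progression from serious adverse event reporting. Section 9.3 limits serious adverse event reports after 30 days to suspected causal relationships.

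Finally, an analysis plan that is not shown could define last contact more narrowly. But the protocol fixes the EFS rule itself, in the same terms as OS, and an analysis plan cannot recover status that visit 888 never asked for.

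**Conclusion.** The point holds as a should-fix. As written, the rule credits event-free time during which relapse and second malignancy are not scheduled to be recorded.

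The direction is certain: upward. The size is not, because it depends on the number and timing of survival-only patients, which the protocol does not give. At shares of 5-10% the 5-year effect is about 0.4 to 1 point, small beside a 13-point half-width. Estimates later than year 5 are more exposed, because survival-only contact is then the scheduled state. Sampling error does not excuse the bias, which runs one way and does not shrink with more patients. The figures rest on constant hazards, the cohort 5 rates, switching unrelated to prognosis and no ascertainment after the switch.

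**What to change.** 1. **Table 7-1, visit 888:** add relapse (yes/no, date) and second malignancy (yes/no, date). With these completed, last known disease status normally coincides with last contact and the problem largely disappears.
2. **Section 7.7.4.1:** censor patients without an event at the last date on which both relapse and second-malignancy status were known. Keep last contact for OS only.
3. **Deaths after disease status lapsed:** where status was not updated before a later death, censor at the last known status in the primary EFS analysis, and count such deaths as events in a sensitivity analysis. Define the lapse, so that deaths between yearly updates during full follow-up (up to visit 778) remain events as they are now.

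The cost is a short rule, two eCRF items and slightly shorter EFS follow-up where status is unknown. The third step departs from the literal event definition for a few deaths, which is why the sensitivity analysis is needed. The items are best added before database lock, while sites can still supply the dates.
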